5. STUDY COMMITTEES

5.1. Steering Committee

The Steering Committee (SC) will include the chairperson, the Principal Investigator (PI), key representatives from the Sponsor and its designees (for example, from the organization(s) conducting the study as delegated by the Sponsor), and key representatives from each region who are deemed to have clinical and methodological expertise (national coordinators).

The SC has overall responsibility for:

- Scientific and strategic direction for the trial. The SC must address and resolve all scientific issues regarding the conduct of the trial. All sub-studies must be approved by the SC.
- The execution of the study protocol, and the reporting and publication of the study results.
- Logistical coordination of the different study committees.

The SC will meet at least twice per year.

5.2. Study Operations Committee (SOC)

The Study Operations Committee (SOC) is responsible for ensuring that study execution and management is of the highest quality, and will monitor recruitment, compliance, and the adjudication process and address the day to day issues arising from the trial. The SOC will be composed of representatives from the Sponsor and the organization(s) conducting the study (as delegated by the sponsor). This committee will meet by telephone and/or in person on a monthly or bimonthly basis, and each meeting will be documented with minutes.

5.3. Clinical Event Committee (CEC)

The CEC is composed of multidisciplinary medical experts. This committee will be responsible for blindly validating all the primary and secondary efficacy outcome events

reported by the investigators (event adjudication). The committee will create a charter with details of the adjudication process and methods based on the definitions of the events.

5.4. Data Monitoring Committee (DMC)

A DMC will be instituted for this study in order to ensure its ongoing safety and to oversee and review the interim analysis. Recommendation for trial continuation will be guided by monitoring boundaries at an interim analysis at which a formal efficacy analysis is performed as well as safety evaluations at all safety data reviews. Members of the DMC will not otherwise be participating in the trial. The committee will include at least one cardiologist and one independent statistician. A DMC Charter will be drafted and approved by the DMC and the Steering Committee. The Charter will provide details regarding the interim analysis and monitoring plan.

6. STUDY PROCEDURES

6.1. Assessment Schedule

A detailed schedule of procedures is provided in Appendix A.

6.1.1. Screening Period

6.1.1.1. Screening Visit (Visit 1)

Patients will come to the Research Site for Visit 1. They will be instructed to fast for at least 10 hours before their visit.

If patients qualify for randomization based on the procedures at Visit 1, they need to be randomized within 42 days after Visit 1. The following procedures will be performed at the screening visit:

- Obtain signed informed consent
- Assign the patient a patient number
- Obtain medical, surgical and family history
- Record demographics
- Obtain height, weight, and body mass index
- Obtain vital signs (systolic and diastolic blood pressure, heart rate, respiratory rate, and body temperature)
- Obtain a 12-lead electrocardiogram
- Evaluate inclusion/exclusion criteria
- This includes procedures and (fasting) blood samples (for example, hs-CRP, calculated creatinine clearance) as needed to determine the CV risk category (see inclusion criteria)
- Obtain fasting blood samples for chemistry and hematology testing
- Obtain a fasting blood sample for the lipid profile (TG, TC, HDL-C, LDL-C, non-HDL-C, VLDL-C)

- Perform a urine pregnancy test on women of childbearing potential
- Record concomitant medication(s)
- Instruct patient to fast for ≥ 10 hours prior to the next visit

6.1.1.2. Screening Visit (Visit 1.1)

Some patients will skip Visit 1.1: Patients who qualify for study participation after Visit 1 because they meet all inclusion criterion and none of the exclusion criteria, may return to the Research Site for Visit 2 to be randomized and to start the treatment/follow-up period of the study. For these patients, Visit 2 will occur soon after Visit 1.

Patients, who do not qualify at Visit 1, may return to the Research Site for a second qualifying visit (Visit 1.1) at the discretion of the investigator. At Visit 1.1, procedures that caused failure of eligibility at Visit 1 will be repeated. Patients will be eligible for randomization after Visit 1.1 if they meet all inclusion criteria and if they no longer fail the exclusion criteria. If patients are evaluated at Visit 1.1 and qualify for randomization based on the repeated procedures at Visit 1.1, they need to be randomized within 60 days after Visit 1.

For some patients, Visit 1.1 will be mandatory at least 28 days after Visit 1 in order to check eligibility. These are patients who at Visit 1 started treatment with a statin, changed their statin, changed the daily dose of their statin, started to washout prohibited medications or started a stabilization period with certain medications (see inclusion/exclusion criteria for details). Any of these changes at Visit 1 may affect the qualifying lipid levels and therefore, patients will need to have Visit 1.1 to determine whether they qualify based on lipid level requirements (TG and LDL-C) determined at Visit 1. Other procedures that caused failure of eligibility at Visit 1 will also be repeated at Visit 1.1.

The following procedures will be performed at the screening visit:

- Obtain vital signs (systolic and diastolic blood pressure, heart rate, respiratory rate, and body temperature)
- Evaluate inclusion/exclusion criteria; only those evaluations will be repeated that deemed the patient not eligible on Visit 1.
- Obtain fasting blood samples for chemistry and hematology testing. Only those samples will be obtained that deemed the patient not eligible on Visit 1.
- Obtain a fasting blood sample for the lipid profile (TG, TC, HDL-C, LDL-C, non-HDL-C, VLDL-C) if the patient was deemed not eligible on Visit 1. This includes patients who at Visit 1 started treatment with a statin, changed their statin, changed the daily dose of their statin, started to washout prohibited medications or started a stabilization period with certain medications (see inclusion/exclusion criteria for details). These patients will have a fasting blood sample collected at Visit 1.1 for the qualifying lipid values (TG and LDL-C), and the TG and LDL-C inclusion criteria will be evaluated.
- Record concomitant medication(s)

6.1.2. Treatment/Follow-Up Period

Every attempt should be made to complete the follow-up visits during the defined window periods.

6.1.2.1. Randomization visit (Visit 2; Day 0)

Qualified patients will return to the Research Site for Visit 2.

The following procedures will be performed at Visit 2:

- Perform physical examination
- Obtain weight
- Obtain vital signs (systolic and diastolic blood pressure, heart rate, respiratory rate, and body temperature)
- Measure waist circumference (one of the factors to diagnose metabolic syndrome)
- Obtain a 12-lead electrocardiogram
- Evaluate inclusion/exclusion criteria
- Obtain fasting blood samples for:
 - Chemistry and hematology testing
 - Lipid profile (baseline)
 - Biomarker assays (baseline)
 - Genetic testing (optional blood sample)
 - Archiving (in countries and at sites approved by IRB/IEC and dependent on country regulations)
- Perform a urine pregnancy test on women of childbearing potential (must be negative for randomization)
- Dispense study drug and record randomization number
- Instruct patient on how to take study drug
- Administer study drug - Note: Study drug should be taken orally with food following the collection of all fasting blood samples
- Assess for and record adverse events
- Record concomitant medication(s)
- Instruct patient:
 - To bring all study supplies with them to the next visit
 - Not to take study drug on the morning of their next visit
 - To fast for ≥ 10 hours prior to the next visit

6.1.2.2. Visit 3 (Day 120; ~4 Months)

Patients will return to the Research Site for Visit 3 on Day 120 ± 10 days.

The following procedures will be performed:

- Perform physical examination
- Obtain weight
- Obtain vital signs (systolic and diastolic blood pressure, heart rate, respiratory rate, and body temperature)
- Obtain fasting blood samples for:
 - Chemistry and hematology testing
 - Lipid profile
- Review study drug compliance by unused capsule count; discuss with and counsel patients about compliance if needed
- Administer study drug - Note: Study drug should be taken orally with food following the collection of all fasting blood samples
- Assess and record efficacy events
- Assess for and record adverse events
- Record concomitant medication(s)
- Instruct patient:
 - To bring all study supplies with them to the next visit
 - Not to take study drug on the morning of their next visit
 - To fast for ≥ 10 hours prior to the next visit

6.1.2.3. Visits 4, 5, 6 and 7

At Visit 4: Day 360 ± 10 ; Visit 5: Day 720 ± 10 ; Visit 6: Day 1080 ± 10 ; and Visit 7: Day 1440 ± 10 , the following procedures will be performed:

- Perform physical examination
- Obtain weight
- Obtain vital signs (systolic and diastolic blood pressure, heart rate, respiratory rate, and body temperature)
- Measure waist circumference (collected at Visit 5 only)
- Obtain a 12-lead electrocardiogram
- Obtain fasting blood samples for:
 - Chemistry and hematology testing
 - Lipid profile
 - Biomarker assays (collected at Visit 5 only)
 - Archiving (in countries and at sites approved by IRB/IEC and dependent on country regulations)

- Review study drug compliance by unused capsule count; discuss with and counsel patients about compliance if needed
- Administer study drug - Note: Study drug should be taken orally with food following the collection of all fasting blood samples
- Assess and record efficacy events
- Assess for and record adverse events
- Record concomitant medication(s)
- Instruct patient:
 - To bring all study supplies with them to the next visit
 - Not to take study drug on the morning of their next visit
 - To fast for ≥ 10 hours prior to the next visit

6.1.2.4. Additional Visits

The end date of the study is expected for Day 1800 but the actual end date will be dependent on the determination of the study end date by the DMC. The study end date is determined to be when approximately 1612 primary efficacy events have occurred. If the actual study end date is later than the expected end date, additional visits will be planned between Visit 7 and the Last Visit with a maximum of 360 ± 10 days between visits. If the actual study end date is sooner than the expected end date, fewer visits will occur, and the last visit (See Section 6.1.2.5) will occur sooner.

On additional visits the same procedures will be performed as listed in Section 6.1.2.3. Irrespective of the number of additional visits, after the DMC has established the end of the study date, there will be a last visit with procedures as listed in Section 6.1.2.5.

6.1.2.5. Last Visit – End of Study

All patients will complete the study at the same time (within a 30-day window after the study end date), irrespective of the date that they were randomized. The end date of the study is planned for Day 1800 but the actual end date will be dependent on the determination of the study end date by the DMC when approximately 1612 primary efficacy events have occurred (event-driven trial). For each patient, the last visit may occur within 30 day after the actual study end date as determined by the DMC. However, for the efficacy endpoints based on CV events, only events occurring up to and including the scheduled actual study end date will be included in the efficacy analyses.

A final follow-up visit is required for all patients. In the rare cases that a final follow-up visit cannot occur within the 30-day timeframe following the study end date, any attempt to contact the patient must be recorded on a special contact form, until/unless appropriate information is obtained.

At the Last Visit, the following procedures will be performed:

- Perform physical examination
- Obtain weight

- Obtain vital signs (systolic and diastolic blood pressure, heart rate, respiratory rate, and body temperature)
- Measure waist circumference
- Obtain a 12-lead electrocardiogram
- Obtain fasting blood samples for:
 - Chemistry and hematology testing
 - Lipid profile
 - Biomarker assays
 - Archiving (in countries and at sites approved by IRB/IEC and dependent on country regulations)
- Determine study drug compliance by unused capsule count
- Assess and record efficacy events
- Assess for and record adverse events
- Record concomitant medication(s)

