12.2.4.6. Interim Efficacy Analysis

One interim analysis will be performed for the primary efficacy endpoint using best available data (adjudicated events and site reported endpoints) based on data when approximately 60% of the total number of primary endpoint events is reached. The interim analysis will be based on a group sequential design that includes early stopping rules for benefit while preserving the overall Type I error rate (O'Brien-Fleming). This allows for interim analysis and preserves the overall Type I error probability of $\alpha=0.05$ for the primary endpoint.

Approximately 1612 primary efficacy endpoint events are planned to be observed during the trial, based on sample size calculation assumptions. Therefore, the interim analysis will occur after at least 967 primary efficacy endpoint events have been observed. According to this

boundary, the critical p-value at the interim analysis has to be $p \leq 0.0076$, resulting in the final evaluation p-value of 0.0476.

The interim results of the study will be monitored by an independent DMC. The analyses will be performed by the independent statistical group unblinded to the treatment assignment. The results will be reported only to the DMC. The unblinded information will not be released to sponsor under any circumstance before the completion of the study. Specific statistical guidelines for data monitoring will be discussed and formalized in a separate Interim Statistical Analysis Plan and DMC Charter.

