12.3. Sample Size Determination

Sample size estimation is based on the assumption that the primary composite endpoint (time from randomization to the first occurrence of CV death, non-fatal MI, non-fatal stroke, coronary revascularization, or unstable angina requiring hospitalization) would be relatively reduced by 15%, from an event rate by 4 years of 23.6% in the placebo group to 20.5% in the AMR101 group. It is expected that a minimum of 1612 primary efficacy endpoint events will be required during the study. A total of approximately 6990 patients are needed to be able to detect this difference at 4.76% significance level (because of the interim analysis described in Section 12.2.4.6) and with 90% power, assuming an 18-month enrollment period and a median follow-up of 4 years. The current sample size calculation is based on an estimated placebo yearly event rate of 5.9% (23.6% over 4 years). To protect against the possibility that the actual placebo event rate is lower than estimated, an extra 1000 patients will be enrolled (approximately 7990 patients in total). By adding the extra 1000 patients, the event rate in the placebo group could be 5.2% per year (20.8% over 4 years) without having to modify the other sample size assumptions.

Since this is an events-driven trial, the ‘sample size’ is the number of events rather than the number of patients. The number of events that occur depends primarily on three factors: how many patients are enrolled, the combined group event rate, and how long the patients are followed. Because of the difficulty in predicting the combined event rate, the sponsor will monitor that event rate as the trial progresses. If the combined event rate is less than anticipated, either increasing the number of patients, extending the length of follow-up, or a balance of adjusting both factors may be necessary to achieve the sample size of 1612 events.

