Before completing the enrollment phase of the trial, *i.e.* approximately 3- to 6-months prior to the projected enrollment of the 7990th patient, the actual event rate based on pooled, blinded accumulation of primary efficacy endpoint events will be calculated and plotted. If those analyses suggest the number of patients with at least 1 adjudicated, primary event (and appropriately accounting for patients with potential primary events for which the adjudication process is then incomplete) is consistent with projections, then the study could continue toward the protocol-specified target enrollment of 7990 patients. However, if the number of such events appears less than, and inconsistent with projections, the Sponsor will consider (under blinded conditions) re-calculating the number of patients needed to achieve the target number of events within the desired timeline or extend the follow-up period. If the projected increase in number of patients is $\leq 25\%$ of the original 7990 target population, the Sponsor may, with documented approval of both the REDUCE-IT Steering Committee and the Data Monitoring Committee, extend enrollment to the revised target number without need for an additional protocol amendment. Under those conditions, all principal investigators, ethics committees, and regulatory authorities associated with the protocol will be promptly notified of the action. Should the projected increase in number of patients be more than 25% above the original 7990 target (*i.e.* more than 1998 additional patients) a formal protocol amendment will be initiated.

If the number of patients to be studied is increased, the enrollment phase will be extended to allow enrollment of the additional patients.

At completion of study enrollment, the actual number of patients randomized may vary from the target number (either original or revised) as a result of the inherent lag between the date the last patient started screening and the date the last patient was randomized.

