9. Safety Laboratories — Complete Blood Count: Includes RBC, Hgb, Hct, WBC and differential, and platelet count. Biochemistry includes total protein, albumin, alkaline phosphatase, ALT, AST, total bilirubin, glucose, calcium, electrolytes (sodium, potassium, chloride), blood urea nitrogen (BUN), serum creatinine, uric acid, creatine kinase, HbA1c. Safety labs may be repeated as deemed necessary by the Investigator.
10. TG, TC, HDL-C, LDL-C, non-HDL-C, and VLDL-C.
11. Fasting blood sample that will be stored for future genetic testing at the discretion of the sponsor. This sample is optional as local regulations may prohibit genetic samples to be collected or shipped outside the country, or patients may not consent.
12. Used at the sponsor's discretion to perform repeat analyses described in the protocol or to perform other tests related to cardiovascular health.
13. Site personnel will contact each patient by telephone in-between Visit 2 and Visit 3 and between Visit 3 and Visit 4. After Visit 4 contact will be made every 3 months. The purpose of the contact is to collect information about efficacy events, adverse events, concomitant medications, confirm patient's current address and contact information and remind patients about taking their study medication and logistics for the next visit.
14. The last visit (LV) may occur within 30 day after the study end date as determined by the DMC; the study end date is tentatively schedule for Day 1800 but the actual date as determined by the DMC may be different.

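### The study end date, and so the efficacy cut-off, is set by the one committee that receives unblinded interim results, with no count-only rule or tolerance

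*Combined protocol and SAP*

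**What the plan says.** All references are to protocol Amendment 1 (16 May 2013). Only the cover of Amendment 2 (8 July 2016) is in the supplied text.

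- **Who sets the date.** Section 6.1.2.5 makes the end date "dependent on the determination of the study end date by the DMC when approximately 1612 primary efficacy events have occurred". Section 6.1.2.4 schedules the last visit "after the DMC has established the end of the study date". Appendix A footnote 14 gives Day 1800 as tentative and adds that "the actual date as determined by the DMC may be different". The 2011 protocol gave the same task to the DSMB.
- **What the date controls.** Under Section 6.1.2.5, "only events occurring up to and including the scheduled actual study end date will be included in the efficacy analyses".
- **Who knows the treatment difference.** Section 12.2.4.6 has the interim analysis "performed by the independent statistical group unblinded to the treatment assignment" and states: "The results will be reported only to the DMC". Apart from that statistical group, the DMC is the only body that holds comparative efficacy data.
- **The target.** Section 12.3 says "a minimum of 1612 primary efficacy endpoint events will be required during the study", whereas 6.1.2.4 and 6.1.2.5 treat 1612 as approximate. No section says whether the triggering count is of adjudicated events (as in the final analysis, 12.2.4) or also includes site-reported ones (as at the interim, 12.2.4.6).
- **Blinded monitoring already planned.** In Section 12.3 the sponsor follows the combined event rate during the trial and reviews pooled, blinded primary events to decide on enrolment and length of follow-up.

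**The concern.** The final test at 0.0476 preserves the overall 5% only if the cut-off does not depend on the observed difference. Here the cut-off is chosen by a committee that has seen that difference at about 967 events, and it is chosen around a target of undefined width. Choosing among dates near 1612 with that knowledge amounts to a data-dependent stopping rule that the boundaries do not cover.

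The decision needs nothing that only the DMC has. It turns on a pooled event count that the sponsor already tracks under blinded conditions. Giving it to the unblinded committee therefore brings no benefit and invites a challenge to the primary result: no one could later demonstrate from the protocol that the date was chosen on the count alone.

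**Working it through.** **Inputs.** Interim at 967 of 1612 events with boundary p ≤ 0.0076 (12.2.4.6); final level 0.0476, two-sided (12.2.4.2); 90% power and a 15% relative reduction, taken as a hazard ratio of 0.85 (12.3); 1:1 allocation (3.8).

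**Step 1: reproduce the plan's figures.**
- Events (Schoenfeld): D = 4(z₁ + z₂)² / (ln HR)², with z₁ = 1.981 (two-sided 0.0476) and z₂ = 1.282 (90% power). This gives 4 × 10.644 / 0.02641 = 1612.
- Interim boundary (O'Brien-Fleming-type spending at 60% information): 4[1 − Φ(2.2414/√0.60)] = 4[1 − Φ(2.894)] = 0.0076.
- Overall alpha with a fixed cut-off at 1612: a bivariate normal with correlation √(967/1612) and critical values 2.669 (interim) and 1.981 (final) gives 0.0500.

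The plan's arithmetic is correct for a cut-off that does not depend on the difference.

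**Step 2: worst case with the documented information.** Suppose the committee knows the interim statistic z at 967 events, has not stopped, and picks the cut-off D in a window so as to maximise rejection under the null. Then

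α = P(|Z| ≥ 2.669) + ∫ max over D of {1 − Φ[(1.981√D − z√967)/√(D − 967)] + Φ[(−1.981√D − z√967)/√(D − 967)]} φ(z) dz,

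integrated over |z| < 2.669. The documents give no window, so the widths below are assumptions.

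| Window | Events | Worst-case overall alpha |
|---|---|---|
| fixed | 1612 | 5.00% |
| ±1% | 1596–1628 | 5.05% |
| ±2% | 1580–1644 | 5.10% |
| ±5% | 1531–1693 | 5.25% |
| 1612 as a minimum, +5% | 1612–1693 | 5.13% |

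**Step 3: what a larger figure would need.** If the difference were also followed inside the window and the trial cut as soon as it crossed 1.981, simulation under the null (1,000,000 runs, steps of 4 events) gives overall alpha of about 6.0% (±1%), 6.6% (±2%) and 7.9% (±5%).

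**Step 4: power.** At HR 0.85 and level 0.0476, power is 88.5% at 1531 events, 90.0% at 1612 and 91.3% at 1693. The choice of cut-off matters little for power.

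**Step 5: timing of the enlargement decision.** Section 12.3 also has the DMC co-approve any increase in enrolment, so it is worth asking whether interim results could exist by then. The review comes 3 to 6 months before the 7990th patient, that is, at months 12 to 15 of an 18-month enrolment. Assume uniform accrual. The placebo hazard is −ln(1 − 0.236)/4 = 0.0673 per year; multiplied by 0.85 this is 0.0572; the average is 0.0622.
- Month 12: 7990 × 12/18 = 5327 patients, mean follow-up 0.5 year: 5327 × 0.5 × 0.0622 ≈ 166 events.
- Month 15: 7990 × 15/18 = 6658 patients, mean follow-up 0.625 year: 6658 × 0.625 × 0.0622 ≈ 259 events.

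Allowing for patients who have already had an event lowers these to about 162 and 252. Both are far below 967.

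**The case against.** The strongest reply is that the stated trigger is an event count, not a treatment difference. Section 12.2.4.6 plans one efficacy look, at about 967 events, and Section 5.4 ties formal efficacy analysis to that look; the other DMC reviews are for safety. This stands. A reader might infer that the DMC would watch the difference near the end, with alpha of about 6% or more. The documents do not support that reading: it needs efficacy looks that are not planned. The interim-only figures are the relevant ones, and even they assume deliberate choice.

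A reader might also infer that the enlargement approval in Section 12.3, "with documented approval of both the REDUCE-IT Steering Committee and the Data Monitoring Committee", exposes a second decision to interim results. That does not hold either. The enlargement decision is the sponsor's, taken on pooled blinded data. On the planned timeline it falls at about 160 to 250 events, before any interim efficacy result exists. Removing the DMC's approval would take away the independent approver, since the Steering Committee includes sponsor representatives (5.1).

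Finally, the DMC Charter and the Interim SAP (5.4, 12.2.4.6) may contain a count-only rule, and Amendment 2 may have changed the text. That is a real limit, but it does not alter what Amendment 1 says in three places.

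**Conclusion.** The point holds as a gap in the protocol's safeguards. Amendment 1 gives the choice of the efficacy cut-off to the one committee that holds the interim treatment difference, without a tolerance and without limiting it to the pooled count. Independence of the cut-off from the result therefore cannot be shown from the protocol. Nothing in the text says the DMC would act on the difference.

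On the documented information the worst case is an overall two-sided alpha of about 5.1% (±2%) to 5.25% (±5%) against 5.00%. These figures rest on assumed windows, knowledge of the 967-event result only, and a cut-off chosen to maximise rejection. Values of about 6% or more would need unplanned looks. The numerical risk is small. The change is worth making because it removes an avoidable challenge to the primary analysis at almost no cost, provided the documents not supplied do not already close the gap.

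**What to change.** - In 6.1.2.4, 6.1.2.5 and Appendix A footnote 14, have the blinded sponsor and Steering Committee declare the end date in advance, as the projected date of the 1612th patient with a first CEC-confirmed primary event, using pooled blinded counts only.
- State a tolerance around 1612. A projected date will not land exactly on the target, so the permitted range should be written down beforehand.
- Inform the DMC of the date. Limit its part in ending the trial to safety and the interim efficacy boundary.
- Reconcile the minimum of 1612 in 12.3 with the approximate 1612 in 6.1.2.4 and 6.1.2.5.
- Leave the enlargement approval in 12.3 as it is.
- First check the DMC Charter, the Interim SAP and Amendment 2. If one of them already has a count-only rule, refer to it in the protocol.

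The cost is protocol wording and a matching line in the charter. No new data are needed, because the sponsor already monitors the pooled event rate.
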